### **3.0 Inclusion and Exclusion Criteria\***

- 3.1 Screening will be done concurrently with the written informed consent process through a self-reported assessment.
- 3.2 Inclusion: Participants must be current first or second year Doctor of Physical Therapy (DPT) students in the School of Allied Health Professions (SAHP) at LSU Health Shreveport (LSUHS).  
Exclusion: current knee pain or pathology in the dominant leg, and women with known pregnancy.
- 3.3 Regarding the inclusion of persons at increased risk:
  - Adults unable to consent: excluded due to not meeting inclusion criteria
  - Individuals who are not yet adults (infants, children, teenagers): excluded because this is not our target population
  - Pregnant women: excluded due to creating greater than minimal risk
  - Prisoners: excluded due to not meeting our inclusion criteria

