to attend an initial data collection session in the rehabilitation faculty clinic and the motion analysis lab 2-217 in the SAHP at LSUHS. Participants will meet in the rehabilitation faculty clinic and age, sex, height, weight, BMI, and dominant lower extremity (LE) will be recorded by DF or EM. The dominant LE is defined as the leg that they usually use to kick a soccer ball. Participants will take the elevator to the second floor and report to 2-217 for sEMG and FSDT data collection. During this time, sEMG electrodes will be applied to the gluteus maximus and medius of the dominant leg, following the placement criteria from *The ABC of EMG* by EM (for female participants) or DF (for male participants) and an MVIC for each muscle will be performed and recorded, with resistance by CH. Participants will be instructed on the procedure for the FSDT by CH prior to completing the test. The FSDT consists of five consecutive repetitions of a forward step down from a 20cm step, with one score given for the whole set of five repetitions. The two student investigators (CH and MS) will both score and average the number between the two scores. sEMG data and FSDT scores will be collected before and after the 8 week HEP. After the initial FSDT is completed, the participant will be educated on the HEP and the compliance chart by MS. The HEP will be a combination of hip musculature activation exercises used by previous researchers that show an increase in hip muscle recruitment. Core activation via a side plank will be added to the clam exercise and the side-lying hip abduction exercise. The HEP consists of five hip activation exercises, clams, clams with trunk activation via side-plank, side-lying hip abduction, side-lying hip abduction with trunk activation via side-plank, and hydrants. The participants will perform isometric contractions of these exercises for up to one minute on the LE used for testing. Once the participant is able to hold all of these exercises for one minute without a break, the participant will advance to the next step, adding a yellow theraband and completing the same exercises. If the participant is able to isometrically hold these five exercises for one minute with a yellow theraband, the participant will progress to a red theraband and repeat the process of working towards one minute holds of each exercise. Each participant will demonstrate the exercises of the HEP to ensure proper form and be informed on the proper progression of the exercises. A compliance chart will be given to the participants to track every time they perform the HEP. Previous authors have used compliance charts to measure this variable in preparation for a dose-response analysis for activation programs. The participants will take home their HEP, a compliance chart, and a yellow and red theraband. The participants will complete the HEP two days a week for eight weeks, with at least two rest days between sessions, and document the completion of the session on the compliance chart. At the end of the 8 week period,

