11.3 See 9.4

11.4 The student investigators (CH and MS) will be educated on the proper procedures of the FSDT, sEMG data collection, and the HEP by the primary investigator (DF) and co-investigator (EM). The FSDT will be analyzed and scored by the two student investigators (CH and MS). The student investigators (CH and MS) will record and average their scores following the completion of five repetitions to improve the quality of the data. The sEMG electrodes will be placed on the female participants by EM and on the male participants by DF. CH will provide the pressure for the MVIC and explain the FSDT procedure to every participant. MS will explain the HEP and the compliance chart to the participants. The primary investigator (DF) is a board-certified orthopedic physical therapist with 10 years of experience, who has published research on this test. The co-investigator (EM) is also a board-certified orthopedic physical therapist with 5 years of experience, who also published research on this test with the primary investigator.

11.5 The data that will be collected during the entire study includes: participant number, height, weight, BMI, sex, leg dominance, FSDT pre and post HEP, recorded FSDT video, sEMG from gluteus medius and maximus on the dominant leg during FSDT pre and post HEP, and compliance. Data storage will follow the guidelines in section 9.4. The data will be stored for the duration of the study and throughout the following semester while analyzing and finalizing data for presentation. The data will be kept up to one year after the completion of the data analysis in event that the research wants to be continued. The only people to have access to this information will be the primary investigators, student investigators, and the co-investigator (DF, EM, CH, MS). All investigators are responsible for the receipt and transmission of the data. Data will be manually transported to DF office room 2-234 in the SAHP at LSUHS. Electronic data will remain on Sharepoint.

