**12.0 Provisions to Monitor the Data to Ensure the Safety of Subjects\***

12.1 N/A

**13.0 Withdrawal of Subjects\***

13.1 Non-study related injury that affects ability to complete HEP or FSDT post intervention.

13.2 After the participant has notified any investigator that they wish no longer to continue or no longer meet the inclusion/exclusion criteria, the investigators will notify the participant that they have been

withdrawn from the study and document the nature for withdrawal and date. The participant will return the compliance sheet to the investigators.

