13.3 N/A

## **14.0 Risks to Subjects\***

14.1 Muscle soreness is a potential side effect that may occur with exercise.

This will be minimized via the progression principles previously outlined in section 9.4.

Participant loss of confidentiality is always a risk; however, this will be minimized via the procedures enumerated in section 9.4.

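### Soreness or injury caused by the home exercise is not collected systematically and is documented only if it leads to withdrawal

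*Combined protocol and SAP*

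**What the plan says.** On risk, section 14.1 states: "Muscle soreness is a potential side effect that may occur with exercise". It relies on the measures in 9.4 to limit this: teaching correct performance, spacing the sessions, and adding resistance only after a hold criterion is met. Section 12.1, on monitoring data for safety, is marked not applicable.

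On exposure, each participant has 16 HEP sessions at home over eight weeks (9.2, 9.3). Participants demonstrate the exercises at the first visit and then advance the load themselves, from no band to yellow to red: "Once the participant is able to hold all of these exercises for one minute without a break, the participant will advance to the next step". No study contact is described between the first visit and the return visit.

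On data, section 11.5 opens "The data that will be collected during the entire study includes: participant number, height, weight, BMI, sex, leg dominance, FSDT pre and post HEP" and goes on to the video, the sEMG and compliance. Section 9.5 gives a similar list. The compliance chart is described as a record of sessions performed (9.2).

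On withdrawal, 13.1 reads: "Non-study related injury that affects ability to complete HEP or FSDT post intervention". Section 13.2 adds a second route, which begins "After the participant has notified any investigator that they wish no longer to continue or no longer meet the inclusion/exclusion criteria". The participant is then told that they have been "withdrawn from the study and document the nature for withdrawal and date". The eligibility rule that this brings in is in 3.2: "Exclusion: current knee pain or pathology in the dominant leg, and women with known pregnancy".

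**The concern.** The plan names one physical risk of its intervention and provides no variable to measure it. Withdrawal is the only event that would generate a note of harm, and the one injury criterion in 13.1 is limited to injury unrelated to the study. Soreness is the kind of harm that often would not make a participant leave, so it would mostly fall outside the record.

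Two things are at stake. First, the report could not say whether the stated risk occurred, how often, or at which resistance. Silence in the data could not be read as absence of harm. Second, Aims 3 and 4 relate compliance to change in FSDT and sEMG. If soreness led some participants to miss sessions and also worsened their week-8 performance, compliance and outcome would be associated for a reason other than dose. Without a reason for each missed session, that explanation could be neither examined nor excluded.

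**Working it through.** **Step 1. Is there a field for soreness, pain or injury?**

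| Place in the plan | What it holds | Harm item? |
|---|---|---|
| 9.3 table of events | Consent, screening, anthropometrics, FSDT, sEMG, HEP, chart | No |
| 9.5 data list | Age, height, weight, BMI, FSDT, sEMG, video, chart | No |
| 11.5 data list for the whole study | As 9.5 without age, plus participant number, sex and leg dominance | No |
| 9.2 compliance chart, as described | Sessions performed | No |
| 9.2 return visit | Hand in chart, repeat sEMG and FSDT | No symptom question described |
| 12.1 safety monitoring | Not applicable | No |

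**Step 2. How could study-related soreness or injury reach the record?**

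- The participant asks to stop: yes, through 13.2, with nature and date.
- The participant reports dominant-leg knee pain or pathology, and so no longer meets 3.2: yes, through 13.2.
- The participant has soreness or pain and stays in: no route is described.
- 13.1 adds nothing here, because it names only injury unrelated to the study.

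**Step 3. How many participants can 13.2 reach?** The plan's recruitment figure (11.2) reproduces as 29 × 1.20 = 34.8, rounded up to 35. At the assumed 20% attrition, 35 × 0.20 = 7 participants leave and 35 − 7 = 28 remain. So 13.2 could supply a reason for at most 7 of 35, and for fewer if some are lost without telling an investigator. The other 28 of 35 (80%) have no described route.

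Planned exposure is 35 × 16 = 560 home sessions, or 28 × 16 = 448 among those who stay. These are planned maxima and say nothing about how often harm occurs.

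**Step 4. What would systematic capture allow?** With zero events in n participants, the one-sided 95% upper limit for the event rate is 1 − 0.05^(1/n):

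- n = 35: 8.2%
- n = 29: 9.8%
- n = 28: 10.1%

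The chance of seeing at least one event in 35 is 1 − (1 − p)^35. The documents give no event rate, so p is assumed:

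- p = 2%: 51%
- p = 5%: 83%
- p = 10%: 97%

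So even 35 participants would support a useful statement about a common event such as soreness. Under the present plan, no rate or bound can be stated.

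**The case against.** The strongest reply is that 13.2 already covers the serious case. It withdraws anyone who wishes to stop or loses eligibility, whatever the cause, and requires the reason and date to be written down. A reader might infer from 13.1 that harm from the HEP would go wholly unrecorded; the documents do not support that. Nor do they support the claim that hip, back or shoulder pain could never be caught: a participant who leaves because of it is documented, and the exclusion in 3.2 could be read to cover any pathology of the dominant leg.

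The safeguards are also more than a hold-time rule, since 9.4 adds instruction in technique and spacing of sessions. The plan rates the study as no more than minimal risk (25.1, 28.2), and no aim concerns safety. The compliance chart is still to be created (9.4), and the consent form was not available for this review. Either could contain a prompt to report pain, and that could not be checked.

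All of this stands as a limit on the claim. It does not remove the gap. Section 13.2 depends on the participant speaking up and misses everyone who stays in. The measures in 9.4 aim to reduce soreness but do not measure it. And 11.5 presents itself as the list for the whole study, without a harm item.

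A further tempting inference is that soreness biases the dose-response. The documents give no figure for this. It is a possible confounder, one of several in a single-arm study, and not a demonstrated one.

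**Conclusion.** The point holds in this form: study-related soreness or injury is captured only when it ends participation and the participant says so. It does not threaten the pre-post comparisons in Aims 1 and 2. It does leave the study unable to report on the risk it names, and unable to separate missed sessions due to soreness from other missed sessions when interpreting Aims 3 and 4. The information cannot be recovered after the sessions have passed.

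At the plan's assumed attrition the gap covers 28 of 35 participants. This rests on the chart being as described in 9.2 and on the consent form adding no reporting procedure. I class it as a cheap improvement: worth making before the forms are printed, with no stated analysis failing without it.

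**What to change.** Add three columns to the compliance chart, with a row for each of the 16 planned sessions so that a missed session also has an entry:

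- soreness or pain: none, mild, or stopped the session, with site;
- reason, if the session was missed;
- band level used (none, yellow, red). No other data item holds this, and it is needed to describe soreness by load.

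Ask about soreness or pain and about missed sessions at the existing week-8 visit. List the new items in 9.5 and 11.5, and report them descriptively, with the number of participants and of sessions as denominators.

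Sections 13.1, 13.2 and 14.1 must also be reconciled on study-related injury. The sponsor decides the content; no withdrawal, stopping or dose rule is proposed here.

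The cost is three columns on a form that participants already complete, a brief question at a visit already planned, and short edits to the text. The downside is slightly more self-report burden.

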13.3 N/A

## **14.0 Risks to Subjects\***

14.1 Muscle soreness is a potential side effect that may occur with exercise.

This will be minimized via the progression principles previously outlined in section 9.4.

Participant loss of confidentiality is always a risk; however, this will be minimized via the procedures enumerated in section 9.4.

14.2 N/A

14.3 N/A

14.4 N/A

## **15.0 Potential Benefits to Subjects\***

15.1 The potential benefits that an individual may experience from taking part in this investigation are improved frontal plane trunk and LE mechanics and improved gluteus medius and maximus activation.

15.2 N/A

## **16.0 Vulnerable Populations\***

16.1 N/A

## **17.0 Community-Based Participatory Research\***

17.1 N/A

## **18.0 Sharing of Results with Subjects\***

18.1 Participants will not receive their individual results.

## **19.0 Setting**

19.1 This study will recruit potential subjects from two cohorts of DPT students. The students are currently attending the SAHP at LSUHS in Shreveport, LA. Recruitment will take place via the procedures outlined in section 9.2. Procedures for research will be performed in the SAHP at LSUHS. Anthropometric data will be collected in the rehabilitation faculty clinic. The motion analysis lab, room 2-217, will be used for the sEMG data collection, FSDT, and education of the HEP. There is no composition or involvement of any community advisory board. The research will not be conducted outside of the organization or its affiliates.

## 20.0 Resources Available

- 20.1 The two student investigators (CH and MS) are DPT students in the SAHP at LSUHS. They will be educated on the procedures of the FSDT, described in Park *et al*, sEMG electrode placement, and data collection and interpretation by the primary investigator (DF), who is a board-certified orthopedic physical therapist with 10 years of experience and the co-investigator (EM), who is a board-certified orthopedic physical therapist with 5 years of experience. The primary (DF) and co-investigator (EM) will assist the student investigators as needed throughout the study, including assisting with data collection and analysis.
- 20.2 The total number of first and second year DPT students enrolled in the SAHP at LSUHS is 67. Given the required N=35, there are enough potential participants to successfully complete this investigation. The student investigators (CH and MS) are enrolled in an independent study for the Fall 2022 semester to receive IRB approval. In the spring of 2023, the data collection portion of the study will begin and be concluded by May 2023. The investigators will be enrolled in Research IV during this semester to allow time to begin working on the poster presentation. Drs. [name] and [name] will each provide 5% FTE for their involvement in the study. During the summer semester of 2023, the student investigators will begin analyzing the data and disseminating. All data analysis will be concluded by August 2023. The motion analysis lab, room 2-217 in SAHP at LSUHS has a treatment mat, sEMG materials and technology, in addition a large open space used for motion analysis. The Rehabilitation Faculty Clinic is located on the ground floor of the SAHP at LSUHS and is where the anthropometric data will be collected. Our study has less than minimal risk. The PI will complete the DOA, including the assigning of roles and responsibilities, and educate each investigator at the time of signing.

## 21.0 Prior Approvals

- 21.1 [name] will need to provide approval for the study to commence since he serves as Chair of the Physical Therapy Department.

## 22.0 Recruitment Methods

- 22.1 One investigator (CH) will inform one DPT cohort in room 1-117 inside the SAHP at LSUHS via word of mouth. During this time, the investigators will obtain informed consent. If the required number of participants is not met (N = 35), the other investigator (MS) will recruit students from the other DPT cohort via word-of- mouth about the investigation and obtain informed consent until the required number of participants are enrolled.

- 22.2 The subjects will be either 1st or 2nd year DPT students in the SAHP at LSUHS.
- 22.3 Potential subjects will first be identified from one DPT by entering room 1-117 of the SAHP at LSUHS. If not enough participants are enrolled, the remainder will be recruited via word of mouth from the other DPT cohort.
- 22.4 N/A
- 22.5 N/A

## **23.0 Local Number of Subjects**

- 23.1 At least 35 participants will be recruited locally.
- 23.2 We hope to enroll 35 participants.

## **24.0 Provisions to Protect the Privacy Interests of Subjects**

- 24.1 Individuals participating in the study will be given an identification number to protect personal identity. Participants will only be expected to interact and provide personal information to the investigators on the study.
- 24.2 There will only be the investigators in the room during data collection, and any questions will be asked individually with the investigators. If another participant is to be in the room learning the HEP, the view will be obstructed with a divider to ensure confidentiality. Any written data will refer to the participants with numbers, not actual names. No previous medical history will be entered into the data collection.
- 24.3 Any information about the subjects will be verbally reported to investigators.

## **25.0 Compensation for Research-Related Injury**

- 25.1 It does not involve greater than minimal risk.
- 25.2 N/A

## **26.0 Economic Burden to Subjects**

- 26.1 There will be no economic burden to the participants. Any required materials will be provided. The only thing the participants will be responsible for is transportation to the facility where study is conducted.

## **27.0 Consent Process**

- 27.1 The consent process will take place in the SAHP at LSUHS in rooms 1-117 and 3-314. There is no waiting period between informing the prospective subject and obtaining the consent. Continued verbal consent will be given during the FSDT/sEMG process both before

and after HEP. We will be using “SOP: Informed Consent Process for Research (HRP-090).”

***Non-English Speaking Subjects***

N/A

***Waiver or Alteration of Consent Process (consent will not be obtained, required information will not be disclosed, or the research involves deception)***

N/A

***Subjects who are not yet adults (infants, children, teenagers)***

N/A

***Cognitively Impaired Adults***

N/A

***Adults Unable to Consent***

N/A

***Adults Unable to Consent***

N/A

## **28.0 Process to Document Consent in Writing**

- 28.1 We will be using “SOP: Written Documentation of Consent (HRP-091).”
- 28.2 Our research does not involve more than minimal risk.
- 28.3 See attached completed informed consent form submitted with this protocol.

## **29.0 Drugs or Devices**

N/A, no device

